**Specific Aim 5: High Risk Screening Performance: CE breast CT and CE-breast MRI.**  
To evaluate the potential of CE-bCT for use in high risk screening (as MRI is used now), CE-bCT ROC performance will be compared against CE-MRI ROC performance. Radiologists will perform full 3D search of the CT and MRI (independently) volume data sets (both with and without contrast) and report

overall probability of malignancy for each modality. Location-specific metrics for potential FROC or LROC analysis will also be captured. Assessment of  $\Delta$ HU will also be performed to quantitatively evaluate predictive performance for malignancy.

Specific Aims 1 and 2 do not require changes in hardware; these two aims are completely focused on post-acquisition image processing techniques (software). Therefore, accrual to the clinical trials as described in Aim 3 can commence on day one of this project. The acquired projection image data from the scanner is always saved, and once the scatter-correction and flat fielding techniques (Aim 1) and optimized reconstruction methods (Aim 2) are finalized, images will be re-reconstructed and become available for the ROC studies on normal-risk screening (Aim 4) and high-risk screening (Aim 5) performance. We believe that this 5 year study will demonstrate that non-contrast bCT can outperform 2D & 3D mammography in breast cancer screening for normal risk patients, and that CE-bCT is (at least) equivalent to CE-MRI for screening high-risk women.

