Numbers of patients needed: To size the studies, we have conducted power analyses [Abbey et al., 2013] based on the Roe and Metz simulation (2,000 runs) for a fixed effects ANOVA model instead of the usual mixed effects model proposed by Dorfman, Berbaum, and Metz (DBM) or correlated error model of Obuchowski and Rockette (Hillis SL, et al., 2005). For the normal-risk bCT-screening study (Aim 4), we have sized the study on the basis of 4 readers, an improvement of 0.05 in AUC, and with average AUC near 0.85 (i.e. AUC = 0.825 vs AUC = 0.875). At these performance benchmarks, 82% power is achieved with 150 positive cases and 250 negative cases. This is a reasonable number of cases given the recruitment procedures described in §D3.1. For the CE-bCT/CE-MRI (high risk screening) comparison (Aim 5), we investigate the non-inferiority of breast CT relative to MRI. We will consider breast CT to be successful in the pilot study if the observed difference in reader-averaged AUC values is greater than -0.025 (i.e.  $AUC(BCT) - AUC(MRI) > -0.025$ ), for a study in which average AUC is approximately 0.85. The Roe and Metz simulation [Abbey, et al, 2013] with 4 readers and 150 cases (60 positive and 90 negative) yields 82% power for finding non-inferiority as defined above in 2,000 independent simulation runs. We expect to be able to recruit at least this many patients for this study based on the recruitment procedures described above.

Informed consent and subject accountability:

There will be a clear accounting of all subjects involved with the study. This includes subjects who are consented, screened, eligible and enrolled as well as ineligible subjects. If a candidate is deemed ineligible for enrollment, the reason for ineligibility will be recorded. There will also be a listing of all patients discontinued or withdrawn from the study after enrollment. These statistics will be reported to the IRB during annual reviews when required.

All subjects participating in this study will provide written consent in the form of the Informed Consent Form. The investigators will allow the candidate to read the consent form and will ask the candidate if they have any questions prior to enrollment. Subject initials, signatures, and date and time will be required in the appropriate places on the form.

Data Handling and Data Management:

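### Aim 5 is labelled non-inferiority but is judged on the observed AUC difference alone, so a CE-bCT truly worse by the full 0.025 margin passes about half the time

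*Combined protocol and SAP*

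**What the plan says.** Section 8, under Numbers of patients needed, says of Aim 5 that "we investigate the non-inferiority of breast CT relative to MRI". Breast CT will be considered "successful in the pilot study if the observed difference in reader-averaged AUC values is greater than -0.025", where the difference is AUC(bCT) minus AUC(MRI), "for a study in which average AUC is approximately 0.85". A simulation "with 4 readers and 150 cases (60 positive and 90 negative" cases) "yields 82% power for finding non-inferiority as defined above in 2,000 independent simulation runs". The same paragraph describes the power work as "based on the Roe and Metz simulation (2,000 runs) for a fixed effects ANOVA model" and gives no variance components.

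Section 2, at the end of Specific Aim 5, states the expectation that the study will show that "CE-bCT is (at least) equivalent to CE-MRI for screening high-risk women".

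Section 6 makes safety and comfort the primary endpoint. Its secondary endpoint compares MRI and CT on sensitivity, specificity and ROC curves, without a margin, an error rate or an interval.

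No section gives an alpha, a confidence limit or a hypothesis test for Aim 5, or the true AUC difference at which the 82% was obtained.

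**The concern.** To claim non-inferiority is to claim that a deficit as large as the margin has been ruled out with a controlled error rate. The Aim 5 rule asks only that the estimate fall on the right side of the margin. An estimate just above -0.025 counts as success even though its confidence interval would extend well below the margin. The 82% is tied to this rule, so it is a pass probability and cannot be read as power in the usual sense.

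What is at stake is the conclusion drawn from a pass. Section 2 expects at least equivalence to CE-MRI for screening high-risk women, and a pass alone does not support that. The primary endpoint and the enrolment of 400 are not affected.

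**Working it through.** **Inputs from section 8.** Margin m = 0.025; success if the observed difference exceeds -m; stated pass probability 82%; 4 readers; 60 positive and 90 negative cases; average AUC about 0.85. For Aim 4: "on the basis of 4 readers, an improvement of 0.05 in AUC, and with average AUC near 0.85", with 82% power at 150 positive and 250 negative cases.

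**Assumptions.** The difference is estimated without bias and is roughly normal. Aim 4 used two-sided alpha 0.05 (not stated; varied in step 1). The true difference behind the Aim 5 figure, d0, is not stated and is varied in step 4.

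**1. Reproducing the 82%.**
- Aim 4 implies SE = 0.05/(1.960 + 0.915) = 0.0174 at 150/250 cases.
- The Hanley-McNeil variance at AUC 0.85 is 2.55 times larger at 60/90, so SE = 0.0174 × √2.55 = 0.0278.
- The point rule at a true difference of 0 passes with probability Φ(0.025/0.0278) = 81.6%, against the stated 82%.
- A rule on the lower limit of the two-sided 95% interval gives Φ(0.025/0.0278 - 1.960) = 14%.
- If Aim 4 used one-sided 0.05, the two figures are about 79% and 12%.

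Only the point rule comes near 82%. This agrees with the plan's own wording, which ties the figure to the definition just given. The conclusion rests on that wording; the back-calculation only corroborates it.

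**2. Pass probability at the margin.** P(pass | d) = Φ((d + m)/SE). At d = -0.025 this is Φ(0) = 50% for any SE.

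**3. The same data judged by a confidence limit.** If the point rule passes 82% of the time at d0, then (d0 + m)/SE = 0.915.
- Lower two-sided 95% limit above -0.025: Φ(0.915 - 1.960) = 14.8%. The share of passes that also clear the margin is 0.148/0.82 = 18%.
- With a one-sided 95% limit instead: Φ(0.915 - 1.645) = 23%, and 23/82 = 28% of passes.
- At a true difference of -0.025: 2.5/50 = 5% of passes, or 5/50 = 10% with the one-sided 95% limit.

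These results depend on the confidence level chosen, but not on d0 or the SE.

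**4. Illustration over d0.** SE = (d0 + 0.025)/0.915. Limits are two-sided 95%.

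| Assumed d0 | SE | Point rule passes at true -0.05 | Observed difference needed for the lower limit to clear -0.025 | Lower-limit power at true 0 |
|---|---|---|---|---|
| -0.01 | 0.016 | 6% | +0.007 | 33% |
| 0 | 0.027 | 18% | +0.029 | 15% |
| +0.01 | 0.038 | 26% | +0.050 | 10% |

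The observed difference needed is -0.025 + 1.96 × SE. For d0 = 0, an estimate just above -0.025 passes with a lower limit of -0.025 - 1.96 × 0.0273 = -0.079.

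**5. Simulation check.** Roe-Metz-type ratings were simulated with 4 fixed readers, 60/90 cases, average AUC 0.85 and 2,000 runs. Variance components are assumed, in the order case, modality-by-case, reader-by-case, error.

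| Components | SE | Point rule, true 0 | Point rule, true -0.025 | Lower two-sided 95% limit, true 0 |
|---|---|---|---|---|
| 0.3, 0.3, 0.2, 0.2 | 0.027 | 83% | 48% | 16% |
| 0.1, 0.1, 0.2, 0.6 | 0.022 | 86.5% | 49% | 20% |
| 0.3, 0.2, 0.2, 0.3 | 0.023 | 87% | 51% | 18% |

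The first set also gives about 84% power for Aim 4, close to the plan's 82%; the other two give 96% and 94%.

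**The case against.** The best defence is that the rule is disclosed and modest. Section 8 calls this a pilot, says the difference is the observed one, and places the definition immediately before the 82%. Any point threshold passes half the time when the truth sits on it. The equivalence sentence in section 2 is worded as a belief, no section says a pass will be reported as equivalence, and the -0.025 rule is not among the endpoints in section 6. The 15% also reflects a choice of confidence level that the plan does not make, and the missing true difference may be in the cited power paper, which was not available.

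Much of this stands. A point threshold is a legitimate go/no-go device, the consequence is limited to how Aim 5 is interpreted, and the fair statement of lower-limit power is 15% to 23% depending on the confidence level. But the word pilot does not change what a pass shows, and section 8 still calls a pass a finding of non-inferiority and attaches power to it. The 50% result needs no confidence level, SE or external paper.

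**Conclusion.** The concern holds. As written, Aim 5 has no non-inferiority test, and its 82% is not the power of one. The chance of passing is about 50% when CE-bCT is truly worse by the full margin, assuming only a roughly symmetric and unbiased estimate. At whatever truth gives the 82%, a two-sided 95% lower-limit rule would pass about 15% of the time under the normal approximation. A pass is therefore compatible with non-inferiority but does not establish it. The SE values and the figures at -0.05 are illustrations, because the plan gives neither the true difference nor the variance components. The plan should be corrected, although its primary endpoint does not depend on this.

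**What to change.** **Preferred.** In section 8, keep -0.025 as a pilot threshold and remove the non-inferiority and power labels. Suggested text:

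> Aim 5 will estimate AUC(bCT) - AUC(MRI) with its two-sided 95% confidence interval. The pilot go/no-go threshold is an observed difference greater than -0.025. With 4 readers and 60/90 cases, the probability of meeting it is 82% if the true difference is [sponsor to state] and about 50% if the true difference is -0.025. Meeting the threshold does not by itself establish non-inferiority.

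In section 2, replace the clause that "CE-bCT is (at least) equivalent to CE-MRI for screening high-risk women" with a statement that the study will estimate the AUC difference between CE-bCT and CE-MRI. Leave the Aim 4 clause alone. The cost is wording, one reported interval and a weaker Aim 5 conclusion. No patients are added.

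**Alternative, if the claim is kept.** Claim non-inferiority only when the lower limit of the two-sided 95% interval exceeds -0.025. Analyse all women with both CE-bCT and CE-MRI. Replace the 82% with power recomputed from the sponsor's own variance components, stating alpha and the assumed true difference.

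This is feasible within planned enrolment, but power would be low and more reads would be needed:
- At 60/90 cases, about 15% at the truth behind the 82%.
- At 150/250 cases with a true difference of 0 and the Aim 4 SE, Φ(0.025/0.0174 - 1.960) = about 30%, or about 25% if Aim 4 used one-sided alpha 0.05.
- To keep 82% at a true difference of 0, the SE must fall to 0.025/(1.960 + 0.915) = 0.0087. That takes (0.0273/0.0087)² = about 9.9 times the 150 cases, or about 1,480, far beyond the planned 400.

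The number of women with both contrast studies is also uncertain, since section 7 allows participation with non-contrast CT only or without MRI. These figures are why relabelling is preferred.

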**9) Data and/or Specimen Banking**

Breast CT images maintained on the laboratory redundant array of independent disks (RAID) will be banked for future image processing development work covered under a separate IRB protocol. The images will not contain any identifiers when they are used for this purpose.

**10) Provisions to Monitor the Data to Ensure the Safety of Subjects**

Physical presence of a licensed technologists, and a physician during the scanning procedure.

The IRB form HRP-214 Reportable New Information will be used to report all serious, unanticipated, and related adverse events to the UC Davis IRB Administration within 5 days of occurrence. This form will also be used to

document minor, anticipated, and/or unrelated adverse events for annual IRB review.

**11) Withdrawal of Subjects**

A subject will be considered to have successfully completed their participation in the study at the conclusion of the scanning procedure. If a subject is removed or withdraws from the study, the specific reasons for discontinuation will be clearly documented in the subject's study file.

**12) Risks to Subjects**

This study involves a small amount of radiation exposure that is typical of other diagnostic tests involving the use of radiation exposure (such as a mammogram).

The amount of radiation exposure received in this study is below the levels that are thought to result in a significant risk of harmful effects.

Risks associated with iodine-based IV contrast injection are as follows:

Minor/Common risks:

- Bruising/infection at the IV site
- Nausea & vomiting
- Urticaria
- Pruritis
- Diaphoresis

Severe/Rare risks:

- Pulmonary edema
- Respiratory arrest
- Cardiac arrest
- Seizures

Moderate/Uncommon risks:

- Faintness
- Facial edema
- Laryngeal edema
- Bronchospasm

Risks associated with gadolinium-based IV contrast injection are as follows:

Minor/Common risks:

- Bruising/infection at the IV site

Severe/Rare risks:

- Nephrogenic Systemic Fibrosis (NSF)

Risks associated with MRI scans are as follows:

Minor/Common risks:

- Claustrophobia

Special IV Contrast Patient Safety Precautions:

A doctor will be present during each contrast-enhanced breast CT and MRI scan to monitor the subject for signs and symptoms of adverse reaction to the contrast injection. A fully-stocked hospital-issued crash kit will be available for emergency treatment. Emergency Medical Services (EMS) will be called for immediate transport to the UCDMC emergency department. Verbal and written post contrast instructions will be provided to the patient at the end of the study visit.

### **13) Potential Benefits to Subjects**

Breast CT images will not be used for diagnosis or treatment planning, and will provide no direct benefit for subjects. Breast MRI scans are the imaging Gold

Standard for breast lesion clinical diagnosis, and the MRI scans performed for this study will be interpreted by a radiologist with the reports available in the subject's medical record. These findings will be available to the subject's referring or primary care physician.

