**Specific Aim 3: Clinical Trial: Imaging women using breast CT and CE-MRI**  
Women with suspicious lesions (BIRADS 4+5) will undergo digital mammography ("2D") and tomosynthesis ("3D") as standard of care workup. Patients who participate will undergo both unenhanced and contrast enhanced breast CT imaging, and also contrast-enhanced breast MRI. Both breasts (affected and unaffected) will be imaged with bCT and MRI. Our facility biopsies 2400 patients over 5 years, and power analysis shows that we will need a total of 400 patients whose images will be used for the normal-risk patient screening comparisons (Aim 4) and for the high risk patient screening comparisons (Aim 5).

**Specific Aim 4: Normal Risk Screening Performance: Comparison of non-contrast bCT with 2D and 2D+3D mammography.** The 4th bCT scanner ("Doheny") is now operational and has four times the spatial resolution of our earliest scanner. Non-contrast bCT has demonstrated better mass-lesion detection performance than mammography (Lindfors, et al, 2008) but using the earlier bCT systems, microcalcification detection was inferior to mammography. Doheny now has vastly improved spatial resolution, and we hypothesize that bCT is (now) equal to or better than screening mammography for microcalcification detection. In this aim, digital mammography and non-contrast bCT images will be compared in a standard receiver operating characteristic (ROC) study. Mammography with Tomosynthesis will also be compared against non-contrast bCT, using ROC methods. A full-search methodology will be used.

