**6) Study Endpoints**

**Primary:** The primary study endpoint will be the assessment of patient safety and comfort at the conclusion of the imaging phase of the study.

**Secondary:** The secondary study endpoint will be the comparison of breast MRI versus breast CT in terms of sensitivity and specificity using biopsy findings as the standard of truth for lesion characterization. True positives & negatives and false positive & negatives will be defined and ROC (receiver operating characteristics) curves will be generated.

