**16) Sharing of Results with Subjects**

Breast CT images and data will not be shared with subjects.

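### Does sending study MRI reports, but not breast CT, into clinical care tilt the Aim 5 reference standard enough to need a plan change?

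*Combined protocol and SAP*

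**What the plan says.** Section 13 treats the two tests differently. For MRI, "the MRI scans performed for this study will be interpreted by a radiologist with the reports available in the subject's medical record", and "These findings will be available to the subject's referring or primary care physician". For bCT, "Breast CT images will not be used for diagnosis or treatment planning"; Section 16 adds "Breast CT images and data will not be shared with subjects".

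The comparison is wide in anatomical scope. Under Specific Aim 3, "Both breasts (affected and unaffected) will be imaged with bCT and MRI". Under Specific Aim 5, "Radiologists will perform full 3D search of the CT and MRI (independently) volume data sets" and give an "overall probability of malignancy for each modality"; location data are captured as well.

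The secondary endpoint in Section 6 compares MRI with bCT "using biopsy findings as the standard of truth for lesion characterization". Section 8 (Statistics and Determination of Study Sample) also makes biopsy the truth for every case. Its cases are BI-RADS 4 and 5 women due for biopsy at the facility, with an assumed 38% positive rate. Section 7 places both scans before a single scheduled biopsy appointment, and Section 5 gives a pathology follow-up of about two to three months.

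Section 8 (Numbers of patients needed) calls bCT successful in Aim 5 if the observed reader-averaged AUC difference, bCT minus MRI, is above -0.025. It quotes 82% power with four readers, 60 positive and 90 negative cases, and an average AUC near 0.85.

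**The concern.** Two tests can be compared fairly only if neither has privileged access to the reference standard. Here the MRI report reaches the treating physician and the bCT result does not. Suppose a woman's scheduled biopsy is benign and MRI shows something elsewhere. A further biopsy could then turn her into a verified positive. A cancer seen only on bCT has no such route; she would stay a negative whom bCT rates high. Because readers search both breasts and give one overall rating, such off-site cancers do enter the score. With a margin of only 0.025, a few relabelled women could turn success into failure and distort the sensitivity and specificity comparison in Section 6.

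**Working it through.** **Inputs.** From Section 8: four readers, 60 positive and 90 negative cases, AUC 0.85, margin 0.025, power 82%, positive biopsy rate 38%. The documents do not give the number of extra cancers, how many would be biopsied, or the reader-study variance components. All of these are assumptions below.

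**1. Which biopsy, and which unit?** In the Aim 5 set, 60/150 = 40%, close to the 38% rate for scheduled biopsies. That fits one case per woman, labelled by the scheduled biopsy. No passage describes an MRI-prompted biopsy; that step is inferred from Section 13.

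**2. The plan's 82%.** Read it as the chance that the observed difference exceeds -0.025 when the true difference is zero. Then SE = 0.025/0.9154 = 0.0273. A Roe-Metz simulation (2,000 runs, four fixed readers, AUC 0.85 for both tests) gave 78.7% to 87.5% over six assumed sets of variance components; two of them gave 82.3% and 81.7%. The figure is attainable but cannot be confirmed without the components.

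**3. Extreme woman-level case.** Let m cancers be visible only to MRI and m only to bCT, all in women with a benign index biopsy, with every MRI-only cancer biopsied. A test rates a cancer it cannot see like a negative, so a pairwise comparison drops from 0.85 to 0.50, a loss of 0.35. Positives become 60 + m and negatives 90 - m. Then

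bCT minus MRI = -0.35m/(60 + m) - 0.35m/(90 - m),

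and the chance of success is Phi((0.025 + difference)/0.0273).

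| m | Expected difference | Chance of success |
|---|---|---|
| 0 | 0 | 82% |
| 1 | -0.0057 - 0.0039 = -0.0097 | 71% |
| 2 | -0.0113 - 0.0080 = -0.0192 | 58% |
| 3 | -0.0167 - 0.0121 = -0.0287 | 45% |

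The arithmetic is sound, but m = 3 means six extra cancers in 90 women (6.7%), each fully visible to one test and wholly invisible to the other.

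**4. Milder woman-level case.** In a simulation with correlated ratings (2,000 runs per setting), both tests could see the extra cancers, and these counted only if a separate clinical MRI read was positive. With four extra cancers the mean difference was -0.003 and the chance of success 80.9%, against 82.6% with correct labels. With eight it was -0.005 and 78.2%, against 83.6%.

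**5. Lesion level.** Section 6 speaks of lesions, and Aim 5 captures locations. MRI-prompted biopsies that prove benign would then count as MRI false positives, while bCT-only false positives would never be verified. With about 12 to 20 extra biopsies, of which 13% to 42% were cancer, equal tests showed a mean difference of +0.010 to +0.016 in favour of bCT. A truly inferior bCT (AUC 0.825 against 0.875) met the rule 26% to 35% of the time, against 17% to 19% on index lesions alone. The direction reverses.

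**6. Is index-only truth a cure?** In the model of step 3 with m of each kind, both AUCs become 0.85 - 0.35m/90 and the difference is zero. That depends on equal numbers. Take three MRI-only cancers and no bCT-only ones:

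- All-biopsy labels, which are correct here: -0.35 × 3/63 = -0.0167; Phi(0.0083/0.0273) = 62%.
- Index labels: +0.35 × 3/90 = +0.0117; Phi(0.0367/0.0273) = 91%.

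MRI is penalised for finding real cancers. In the simulation with eight extra cancers and an inferior bCT, index labels raised the chance of success from 17.0% to 23.4%.

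**The case for a change.** The strongest case for acting is that the plan leaves both the reference standard and the unit of analysis open, and that the bias can run either way. An undefined standard could be settled after the readings are known, and a 0.025 margin on a point estimate leaves little room. One sentence of definition, a field recording what prompted each biopsy and a parallel analysis would cost little. There is a further worry: MRI results arrive before the scheduled biopsy and might affect whether it takes place. If half of the biopsies in women with a low MRI rating were not done, the simulated chance of success for an inferior bCT rose from 17%-18% to 23%-26%.

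Some of this stands. MRI does enter care and bCT does not, and no sentence expressly excludes later biopsies or fixes the unit. But no passage says that MRI prompts or cancels biopsies. Recording the trigger changes no result, and it could plausibly be rebuilt: Section 8 keeps biopsy reports, mammography reports and case report forms, Section 13 puts MRI reports in the medical record, Section 7 allows continued record access, and Aim 5 captures locations. A parallel index-truth analysis would not settle the matter, because it carries its own bias whenever one test finds more true off-site cancers.

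**Conclusion.** No change to the plan is called for. What is missing is a detail that analysts would fill sensibly. Section 8 describes women who are going to biopsy, applies that biopsy's positive rate, and then makes the biopsy the truth; Section 7 describes one appointment. On that reading, and provided the scheduled biopsy is done, labels do not depend on MRI and the unequal access disappears.

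If later MRI-prompted biopsies were counted, the effect could be anywhere from nil to material. It is zero with no such biopsies, about -0.003 to -0.005 in AUC for four to eight extra cancers under correlated readings, and -0.029 in the extreme case. All of these sizes rest on assumed counts, and the simulated ones also on assumed variance components. The direction is not fixed: against bCT for woman-level labels with extra cancers only, possibly in its favour at lesion level. The choice between all-biopsy and index-biopsy truth is therefore a fair trade-off, since neither is unbiased in general. A documented, substantial number of MRI-prompted biopsies entering the Aim 5 labels would reopen the question; nothing in the documents shows one.
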